**Table 3 Detailed Schedule of events – Enrolment and treatment weeks with weight assessment**

Time	Treatment period – Enrolment (Week 25) a and Weeks 29, 33, 37, 41, 45, 49, 53, 57, 61, 65, 69, 73, 77, 81, 85, 89, 93, 97 and 101				
	Pre-infusion	Start of infusion (0:00)	Mid-infusion (2:00) b	Stop of infusion (4:00) b	Within 1 hour of completing the infusion (4:01 - 5:00) c
Concomitant therapy	X	X	X	X	X
Physical examination (general appearance and skin)	X				X
Weight d	X				
Vital signs	X		X b		X
Antihistamine e	X				
SOBI003 administration:					
Start of infusion		X			
Stop of infusion				X	
Adverse events	X	X	X	X	X

a. Prior to any study assessment the eligibility criteria must be confirmed and the enrolment informed consent obtained.

b. The SOBI003 infusions are initially given over a period of 4 hours. When no more dose increases are expected, and the intensified study assessments associated with dose adjustments are completed, the infusion period in individual patients may step-wise be decreased at the discretion of the investigator. The minimal infusion period is 1 hour. If the infusion period is decreased to <4 hours (see Section 7.4.5), the vital sign assessment is performed in the middle of the infusion period, i.e. if the infusion period is 2 hours, the vital sign assessment is performed 1 hour after start of infusion.

c. The scheduled assessments will be performed within 1 hour after end of infusion, i.e., timing will be dependent on the infusion period.

d. Weight to be obtained prior to preparation of the SOBI003 infusions solution, either the day prior to the infusion or on the day of infusion.

e. Within 30 to 60 minutes prior to each SOBI003 infusion, a single dose of a non-sedative antihistamine should be administered.

**Table 4 Detailed Schedule of events – Treatment weeks without weight assessment**

Time	Treatment period - Weeks 26, 27, 28, 30, 31, 32, 34, 35, 36, 39, 40, 42, 43, 44, 46, 47, 48, 50, 51 a , 54, 55, 56, 58, 59, 60, 62, 63, 64, 66, 67, 68, 70, 71, 72, 74, 75, 76, 79, 80, 82, 83, 84, 86, 87, 88, 90, 91, 92, 94, 95, 96, 98, 99, 100, 102 and 103 a				
	Pre-infusion	Start of infusion (0:00)	Mid-infusion (2:00) b	Stop of infusion (4:00) b	Within 1 hour of completing the infusion (4:01 - 5:00) c
Concomitant therapy	X	X	X	X	X c
Physical examination (general appearance and skin)	X				X c
Vital signs	X		X b		X c
Antihistamine d	X				
SOBI003 administration:					
Start of infusion		X			
Stop of infusion				X	
Adverse events	X	X	X	X	X

a. Sleep pattern is assessed by actigraph recordings for 7 consecutive days at Weeks 51-52 and 103-104, i.e., the recordings start Weeks 51 and 103, and will cease in the morning of the Week 52 and 104 infusions. An actigraph log is completed during the days of actigraphy.

b. The SOBI003 infusions are initially given over a period of 4 hours. When no more dose increases are expected, and the intensified study assessments associated with dose adjustments are completed, the infusion period in individual patients may be decreased step-wise at the discretion of the investigator. The minimal infusion period is 1 hour. If the infusion period is decreased to <4 hours (see Section 7.4.5), the vital sign assessment is performed in the middle of the infusion period, i.e. if the infusion period is 2 hours, the vital sign assessment is performed 1 hour after start of infusion.

c. The scheduled assessments will be performed within 1 hour after end of infusion, i.e., timing will be dependent on the infusion period.

d. Within 30 to 60 minutes prior to each SOBI003 infusion, a single dose of a non-sedative antihistamine should be administered.

**Table 5 Detailed Schedule of events – Weeks 38 and 78**

Time	Weeks 38 and 78					
	Pre-infusion	Start of infusion (0:00)	Mid-infusion (2:00) a	Stop of infusion (4:00) a	Within 1 hour following infusion (4:01 - 5:00)	Day 8 (Pre-infusion, 168:00)
Concomitant therapy	X	X	X	X	X b	
Physical examination (general appearance and skin)	X				X b	
Vital signs	X		X		X b	
Antihistamine c	X					
SOBI003 administration:						
Start of infusion		X				
Stop of infusion				X		
Adverse events	X	X	X	X	X	
Blood sampling for:						
Safety laboratory	X					
Immunogenicity	X					
HS	X					
PK	X			X d		X e
Urine collection for:	X					
Safety laboratory (Dipstick)	X					
HS	X					

a. The SOBI003 infusions are initially given over a period of 4 hours. When no more dose increases are expected, and the intensified study assessments associated with dose adjustments are completed, the infusion period in individual patients may be decreased step-wise at the discretion of the investigator. The minimal infusion period is 1 hour. If the infusion period is decreased to <4 hours (see Section 7.4.5), the vital sign assessment is performed in the middle of the infusion period, i.e. if the infusion period is 2 hours, the vital sign assessment is performed 1 hour after start of infusion.

b. The scheduled assessments will be performed within 1 hour after end of infusion, i.e., timing will be dependent on the infusion period.

- c. Within 30 to 60 minutes prior to each SOBI003 infusion, a single dose of a non-sedative antihistamine should be administered.
- d. PK sample should be collected as soon as possible following end of infusion.
- e. 168 hour PK sample for weeks 38 and 78 is collected pre-infusion on weeks 39 and 79 respectively.

**Table 6 Detailed schedule of events – Weeks 52 and 104 –Day 1**

Day	Weeks 52 and 104 – Day 1				
	1	1	1	1	1
Time	Pre-infusion	Start of infusion (0:00)	Mid-infusion (2:00) a	Stop of infusion (4:00) a	Within 1 hour of completing the infusion (4:01 - 5:00) b
Concomitant therapy	X	X	X	X	X
Physical examination (general appearance and skin)	X				X
Vital signs	X		X		X
Antihistamine c	X				
SOBI003 administration:					
Start of infusion		X			
Stop of infusion				X	
Adverse events	X	X	X	X	X
Blood sampling for:					
Safety laboratory	X				
Immunogenicity	X				
HS	X				
PK	X			X e	
Future research d	X				
Urine collection for:	X				
Safety laboratory (Dipstick)	X				
HS	X				
Actigraphy (sleep pattern) f	X				

	Weeks 52 and 104 – Day 1				
Day	1	1	1	1	1
Time	Pre-infusion	Start of infusion (0:00)	Mid-infusion (2:00) a	Stop of infusion (4:00) a	Within 1 hour of completing the infusion (4:01 - 5:00) b
Parent/caregiver questionnaires:					
CSHQ f	X				

a. The SOBI003 infusions are initially given over a period of 4 hours. When no more dose increases are expected, and the intensified study assessments associated with dose adjustments are completed, the infusion period in individual patients may step-wise be decreased at the discretion of the investigator. The minimal infusion period is 1 hour. If the infusion period is decreased to <4 hours (see Section 7.4.5), the vital sign assessment is performed in the middle of the infusion period, i.e. if the infusion period is 2 hours, the vital sign assessment is performed 1 hour after start of infusion.

b. The scheduled assessments will be performed within 1 hour after end of infusion, i.e., timing will be dependent on the infusion period.

c. Within 30 to 60 minutes prior to each SOBI003 infusion, a single dose of a non-sedative antihistamine should be administered.

d. Only applicable when separate consent has been provided for future research

e. PK sample should be collected as soon as possible following end of infusion.

f. Sleep pattern is assessed by actigraph recordings for 7 consecutive days at Weeks 51-52 and 103-104, i.e., the recordings start Weeks 51 and 103, and will cease in the morning of the Week 52 and 104 infusions. An actigraph log is completed during the days of actigraphy. Parents should complete the CSHQ upon completion of each actigraph assessment (i.e., at Weeks 52 and 104 this will be during the infusion days).

**Table 7 Detailed schedule of events – Weeks 52 and 104 – Days 2 to 7**

	Weeks 52 and 104 – Days 2 to 7				
Day	2	3	4	5	7 (8 a )
Concomitant therapy	X	X	X	X	X
12-lead ECG					X
Physical examination (complete)					X
Neurological examination					X
Height, weight & head circumference					X
Adverse events	X	X	X	X	X
Anesthesia/sedation i for:					
CSF sampling (PK, ADA, HS, future research b )	X				
MRI (brain, liver, spleen)	X				
Blood sampling for:					
PK	X				X
BSID-III/KABC-II (neurocognition, language, motor function) c			(X) c	(X) c	X c
Parent/caregiver questionnaires:					
VABS-II		X			
PedsQL, incl. Family Impact Module			X		

a. Only PK sampling applicable on Day 8 (168 h after start of infusion). All other assessments are performed on Day 7.

b. Only applicable when separate consent has been provided for future research.

c. In case both BSID-III and KABC-II should be assessed, the BSID-III should be administered first, and there should be at least 2 days between the BSID-III and KABC-II assessments. If only BSID-III or KABC-II is to be assessed this should be done on Day 7.

**Table 8 Detailed schedule of events – Following a SOBI003 dose adjustment - first 3 weeks**

Week	Following a SOBI003 dose adjustment – First 3 weeks												
	1, 2, 3 (following dose adjustment)												
	Day	1	1	1	1	1	1	1	1	1	2	3	8
Time	Pre-inf	0	1:00	2:00	3:00	4:00	4:01 - 5:00	6:00 – 7:00	8:00 - 12:00	24	48	168 (pre-inf)	
Concomitant therapy	X		X	X	X		X	X	X	X	X	X	
Physical examination (general appearance and skin)	X		X	X	X		X	X	X	X	X		
Vital signs	X		X	X	X		X	X	X	X	X		
Continuous pulse-oximetry	→												
Antihistamine	X												
SOBI003 administration													
Start of infusion		X											
Stop of infusion						X							
Adverse events	X	X	X	X	X	X	X	X	X	X	X	X	
Blood sampling for:													
Safety laboratory	X												
Immunogenicity	X a												
HS	X												
PK	X b					X c, d						X d	
Urine collection for:													
Safety laboratory (Dipstick)	X												
HS	X												

a. Only on week 3

b. Collected on Weeks 1 and 3 following dose adjustment.

c. PK sample should be collected as soon as possible following end of infusion.

d. Collected on Weeks 1 following dose adjustment.

**Table 9 Detailed schedule of events – Following a SOBI003 dose adjustment – Weeks 4 and 8**

	Following a SOBI003 dose adjustment – Weeks 4 and 8					
Week	4, 8 (following dose adjustment)					
Day	1	1	1	1	1	8
Time	Pre-infusion	Start of infusion (0:00)	Mid-infusion (2:00) a	Stop of infusion (4:00) a	Within 1 hour of completing the infusion (4:01 - 5:00) b	Pre-infusion next week (168:00)
Concomitant therapy	X		X		X	X
Physical examination (general appearance and skin)	X				X	
Vital signs	X		X		X	
Antihistamine c	X					
SOBI003 administration						
Start of infusion		X				
Stop of infusion				X		
Adverse events	X	X	X	X	X	X
Blood sampling for:						
PK	X			X d		X

a. The SOBI003 infusions are initially given over a period of 4 hours. When no more dose increases are expected, and the intensified study assessments associated with dose adjustments are completed, the infusion period in individual patients may step-wise be decreased at the discretion of the investigator. The minimal infusion period is 1 hour. If the infusion period is decreased to <4 hours (see Section 7.4.5), the vital sign assessment is performed in the middle of the infusion period, i.e. if the infusion period is 2 hours, the vital sign assessment is performed 1 hour after start of infusion.

b. The scheduled assessments will be performed within 1 hour after end of infusion, i.e., timing will be dependent on the infusion period.

c. Within 30 to 60 minutes prior to each SOBI003 infusion, a single dose of a non-sedative antihistamine should be administered.

d. PK sample should be collected as soon as possible following end of infusion.

**Table 10 Detailed PK blood sampling schedule**

Week	Time	No of samples a
Week 38	Pre-infusion	1
	4h / End of Infusion	2
	168h	1
Week 52	Pre-infusion	1
	4h / End of Infusion	2
	Day 2 c	1
	168h	1
Week 78	Pre-infusion	1
	4h / End of Infusion	2
	168h	1
Week 104	Pre-infusion	1
	4h / End of Infusion	2
	Day 2 c	1
	168h	1
At week of dose adjustment b	Pre-infusion	1
	4h / End of Infusion	2
	168h	1
3 weeks after dose adjustment	Pre-infusion	1
4 weeks after dose adjustment b	Pre-infusion	1
	4h / End of Infusion	2
	168h	1
8 weeks after dose adjustment b	Pre-infusion	1
	4h / End of Infusion	2
	168h	1
At early treatment/study termination	Early Termination visit – time point same as immunology sample	1
	30-40 days post Early Termination visit - time point same as immunology sample	1
	If additional immunogenicity samples as part of follow-up- number of samples per time point	1

a If Number = 1; PK blood sample is collected from central venous access port. If Number =2; One PK sample will be collected from the central venous access port and one PK sample will be collected from a peripheral venous line. The PK samples from a peripheral venous line for the End of infusion sample can be excluded if it has been confirmed in the FIH study (SOBI003-001) that the SOBI003 i.v. infusion does not interfere with the PK blood sampling..

b If the dose of SOBI003 is adjusted in a patient, PK blood samples will be collected before infusion, at the end of infusion and 168 hours after start of the infusion at the week of dose adjustment and 4 and 8 weeks after the dose adjustment.

c At the time of CSF sample collection Day 2, a PK blood sample will also be collected. In case the time point for the CSF sample is deviating from the planned time point, the blood samples should be adjusted accordingly.

### 7.5.1.2 Week 25 / Enrolment

The patient is admitted to the hospital the day prior to or on the day of the SOBI003 infusion. This week will be continue directly following last study visit (Week 24) in the FIH study ([SOBI003-001](#)) without any break in treatment. Baseline information collected during the first study will be used for the extension study. Patient demography information will only be collected at Week 25 if there are any changes to the already collected data.

The informed consent process, including the provision of signed consent for study participation, is completed and the patient eligibility is confirmed.

AEs and concomitant medications are captured continuously from Day 1 of Week 25 until study completion. This includes all events observed/diagnosed or reported since the last visit of the FIH study ([SOBI003-001](#)) study (Week 24 / End of study).

Prior to start of the infusion, the following is performed:

- Body weight is obtained either the day prior to the infusion or the day of infusion
- General appearance and skin are assessed (part of physical examination)
- Vital signs are assessed

Within 30 to 60 minutes prior to start of the SOBI003 infusion, a single dose of a non-sedative antihistamine is administered. SOBI003 is administered in accordance with Section 7.4.5.

Vital signs are assessed approximately 2 hours after start of infusion. Within an hour of completion of the infusion, vital signs, general appearance and skin are assessed.

The patient may be discharged from the hospital 1 hour or more after the end of the infusion.

### 7.5.1.3 Weeks 26 to 37, Weeks 39 to 51, Weeks 53 to 77 and Weeks 79 to 103

SOBI003 is administered as weekly infusions; a +/- 1-day window is applied. The patients will return to the hospital the day prior to or on the day of each infusion. AEs and use of concomitant medications during non-hospital stay are captured.

Prior to start of each infusion, weekly vital signs and general appearance and skin are assessed.

At Weeks 29, 33, 37, 41, 45, 49, 53, 57, 61, 65, 69, 73, 77, 81, 85, 89, 93, 97 and 101, body weight is also assessed to determine the SOBI003 dose to be administered during a forthcoming 4-week interval, respectively. The body weight is obtained either on the day prior to the infusion or the day of infusion.

At Weeks 39 and 79, a pre-infusion PK sample will be collected as part of the PK collection from previous visits (Weeks 38 and 78 respectively).

Within 30 to 60 minutes prior to start of each SOBI003 infusion, a single dose of a non-sedative antihistamine is administered. SOBI003 is administered in accordance with Section 7.4.5.

Vital signs are assessed approximately mid-infusion as described in Section 7.5.5.4. Within an hour of completion of the infusion, vital signs and general appearance and skin are assessed.

Prior to discharge at Weeks 51 and 103, the parent/caregiver is given the actigraph and the accompanying actigraph log. The parent/caregiver is instructed to start the sleep assessment 7 days prior to attendance for the 52th and 104th infusion.

The patient may be discharged from the hospital 1 hour or more after the end of each infusion.

#### **7.5.1.4 Weeks 38 and 78**

SOBI003 is administered as weekly infusions; a +/- 1-day window is applied. The patients will return to the hospital the day prior to or on the day of each infusion. AEs and use of concomitant medications during non-hospital stay are captured.

Prior to start of each infusion, vital signs and general appearance and skin are assessed. Blood and urine are collected for safety laboratory and HS assessments, and blood samples are also collected for assessment of immunogenicity and PK.

Within 30 to 60 minutes prior to start of each SOBI003 infusion, a single dose of a non-sedative antihistamine is administered. SOBI003 is administered in accordance with Section 7.4.5.

Vital signs are assessed approximately mid-infusion as described in Section 7.5.4.4. As soon as possible following end of infusion a blood sample is collected for PK evaluation. Vital signs and general appearance and skin are assessed within an hour of completing the infusion.

The patient may be discharged from the hospital 1 hour or later after the end of each infusion.

On Day 7, prior to the next weekly infusion, a blood sample is collected for PK evaluation.

#### **7.5.1.5 Week 52**

SOBI003 is administered as weekly infusions; a +/- 1-day window is applied. The patients will return to the hospital the day prior to or on the day of the last infusion. AEs and use of concomitant medications during non-hospital stay are captured. The actigraph and accompanying actigraph log are collected.

##### **7.5.1.5.1 Week 52, Day 1 Assessments**

Prior to start of the infusion, the following is performed:

- Vital signs are assessed
- General appearance and skin are assessed
- Blood and urine is obtained for safety laboratory
- Blood and urine is obtained for HS assessment
- Blood is obtained for immunogenicity and PK assessments
- When separate consent for future research has been provided, serum samples will also be collected for storage at the central laboratory.

Within 30 to 60 minutes prior to start of each SOBI003 infusion, a single dose of a non-sedative antihistamine is administered. SOBI003 is administered in accordance with Section 7.4.5.

Vital signs are assessed approximately mid-infusion as described in Section 7.5.4.4. As soon as possible following end of infusion, a blood sample is collected for PK evaluation. Vital signs and general appearance and skin are assessed within an hour of completing the infusion.

The parent/caregiver completes the CSHQ questionnaires, preferably during Day 1.

#### 7.5.1.5.2 Week 52, Day 2 to 7 Assessments

On day 2, general anesthesia is applied in accordance with local routines at the study site. CSF sampling for PK, ADA, and HS assessments and MRI scanning of brain, liver and spleen are completed while the patient is anesthetized. The order of the procedures should preferably be as stated. Should this not be feasible for an individual patient, then effort should be made to have the assessments performed in the same order as they were performed in the FIH study ([SOBI003-001](#)). When separate consent for future research has been provided, CSF will also be collected for storage at the central laboratory.

At the time of CSF sample collection Day 2, a PK blood sample will also be collected. In case the time point for the CSF sample is deviating from the planned time point, the blood samples should be adjusted accordingly.

On Day 3, the VABS-II is assessed by parent/caregiver (refer to Section 7.5.3.2).

The parent/caregiver completes the PedsQL questionnaire, preferably during Day 4.

Based on the patient's developmental age, as determined by the VABS-II score, the BSID-III and/or KABC-II tests are conducted for assessment of neurocognition, language and motor function (see Sections 7.5.3.1, 7.5.3.2, and 7.5.3.6, respectively). If *only* BSID-III or *only* KABC-II is to be assessed, then this should be done on Day 7. If *both* BSID-III and KABC-II should be assessed, then the BSID-III should be administered on Day 4 or 5 and the KABC-II on Day 7.

On Day 7, a neurological and a complete physical examination are performed, an ECG is conducted and height, weight and head circumference are obtained. In addition, blood is collected on Day 8 (approximately 168h after start of SOBI003 infusion) for PK analyses as specified in Section 7.5.5.1.

The patient may be discharged from the hospital 1 hour or later after start of the infusion. The patient will then return to the hospital for study assessments as detailed in Schedule of Events (Table 7).

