**Figure 1 Overview for study design for study SOBI003-002**

To secure a close monitoring of the patients and the intensified study assessments at Weeks 52 and 104, and at week(s) of dose adjustments, the minimum hospitalization periods specified in Table 1 are applied:

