**Table 1 Minimum hospitalization periods**

Week	Minimum hospitalization period*
25 to 51, 53 to 103	Admission; day of infusion Discharge; 1 hour or later after the end of each infusion
52 and 104	Admission; day of infusion Discharge; 1 hour or later after the end of infusion
At week(s) of dose adjustments	Admission; day of infusion Discharge; 48 hours after initiation of each of the first 3 infusions**

\* Extended as per local routine for admission/discharge and per patient need as determined by the investigator (eg, concurrent illness, travel distance etc)

\*\* If dose adjustment is a decrease in dose as a result of study dose selection for forthcoming studies, and there are no safety concerns, the patient may be discharged 1 hour or later after the end of each infusion.

An emergency card containing details on how to seek medical help will be provided to each parent/caregiver and they will be instructed to always carry the emergency card. The card will also contain brief details on the study treatment and contact details to site staff in order to secure appropriate medical management of any emergency situation that has to be managed outside the study site.

Depending on the distance and any travelling difficulties, the regular weekly infusions of SOBI003 may be administered at home by a trained study nurse or at a geographically closer satellite site, if judged safe by the investigator and Sobi MD. At weeks with scheduled laboratory or efficacy assessments and during 12 weeks following a dose increase or reduction due to safety, SOBI003 infusions will always be performed at the PI site. If the patient receives all infusions at the PI site, they and their parent(s) may be relocated for parts the study or for the full study duration. The families are reimbursed for travel and, if applicable, for accommodation expenses and caregiver meals. Appointed study coordinators will assist the families with travel and accommodation arrangements.

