### **7.3.5 Specific restrictions/requirements on patients**

The patients are required to visit the site weekly for the SOBI003 infusions and remain at the site for at least 1 hour after the end of the infusion. The hospitalization period may be extended as per local routine for admission/discharge and per patient need as determined by the investigator (e.g., concurrent illness and travel distance).

Following a dose adjustment, patients are hospitalized for at least 48 hours after initiation of each of the first 3 infusions. If dose adjustment is a decrease in dose as a result of study dose selection for forthcoming studies, and there are no safety concerns, the patient may be discharged 1 hour or later after the end of each infusion.

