### **7.4.2 Identity of investigational medicinal products**

SOBI003 is provided as concentrated solution for i.v. infusion, 20 mg/mL, in 5-mL injection vials. Each vial contains 4 mL. Ten vials are packed in one box/outer carton. Vial and outer carton labeling will comply with national regulatory requirements. To facilitate accurate drug accountability, vial-specific numbers are printed on the vial labels.

The drug substance is manufactured by [REDACTED]

[REDACTED]. The drug product is manufactured by [REDACTED]

3 days, then the investigator should discuss with the Sponsor's MD to determine the timing of the next infusion (i.e., whether to await the next scheduled infusion).

Within 30 to 60 minutes prior to each infusion, a single dose of a non-sedative antihistamine should be administered. The antihistamine can either be e.g., cetirizine, levo-cetirizine, loratadine, des-loratadine or fexofenadine, and the administered doses will be in compliance with locally approved labeling. The antihistamine agent is selected at the discretion of the investigator. Antipyretic medication may also be administered, at the discretion of the investigator.

The actual doses of SOBI003 to be administered should be based on the patient's body weight at 4-week intervals (i.e., the actual dose administered at Weeks 25 to 28 is based on the body weight obtained pre-infusion at Week 25, the actual dose administered at Weeks 29 to 32 is based on the body weight obtained pre-infusion at Week 29, etc.). The body weight is obtained either on the day prior to the infusion or the day of infusion. For a body weight < 25 kg, the targeted total infusion volume is 100 mL. For a body weight  $\geq$  25 kg, the targeted total infusion volume is 250 mL. If the infusion bag contains an overfill volume, the infusion should continue until the infusion bag is emptied.

The final concentration of SOBI003 in the infusion bag will be calculated based on the added volume of SOBI003 to the infusion bag, and the total volume in the infusion bag.

The SOBI003 infusions are initially given over a period of 4 hours. When no more dose increases are expected, and the intensified study assessments associated with dose adjustments are completed (Section 7.5.1.7), the infusion period in individual patients may step-wise be decreased at the discretion of the investigator. The minimal infusion period is 1 hour.

Infusion rate schedules are provided in a separate IMP manual.

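### The Week 52 and Week 104 visit text counts the one-hour discharge minimum from the start of the infusion; Table 1 and Section 7.3.5 count it from the end

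*Protocol*

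**What the plan says.** Protocol Section 7.5.1.5.2 (Week 52, Days 2 to 7) closes with: "The patient may be discharged from the hospital 1 hour or later after start of the infusion". Section 7.5.1.6.2 (Week 104) carries the same sentence. In both places the next sentence has the patient return for the Table 7 assessments, so the rule concerns discharge after the Day 1 infusion.

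Three other texts govern the same stay:

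- The text introducing Table 1 names Weeks 52 and 104 and states that "the minimum hospitalization periods specified in Table 1 are applied".
- The Table 1 row for Weeks 52 and 104 reads "Discharge; 1 hour or later after the end of infusion".
- Section 7.3.5 requires patients at the weekly infusions to "remain at the site for at least 1 hour after the end of the infusion".

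The other visit sections agree with Table 1. Section 7.5.1.2 (Week 25) has "The patient may be discharged from the hospital 1 hour or more after the end of the infusion". Section 7.5.1.3 (the routine weeks) has "The patient may be discharged from the hospital 1 hour or more after the end of each infusion". Section 7.5.1.4 (Weeks 38 and 78) has "The patient may be discharged from the hospital 1 hour or later after the end of each infusion".

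Infusions start at 4 hours. Section 7.4.5 allows step-wise shortening under conditions: "The minimal infusion period is 1 hour".

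**The concern.** The two visit sections permit something that the table of minimum stays and the general patient requirements do not. Nothing exempts Weeks 52 or 104. The first footnote to Table 1 only lengthens the stay. The second covers certain dose decreases and still counts from the end of the infusion.

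The hour is a safety-observation rule for children receiving an enzyme infusion. Section 5.2 warns that severe hypersensitivity reactions remain possible and relies on supervision both during and after infusions. It also points to Table 1 when it discusses delayed reactions outside hospital. Staff running a visit are likely to work from the visit section, and here that section gives the weaker rule. A site that followed it could cut the observation hour short and breach Table 1 and Section 7.3.5.

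**Working it through.** No sample size, power or error rate is involved. The check is a comparison of texts and clock arithmetic.

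**1. Count of one-hour discharge statements**

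| Place in the protocol | From end | From start |
|---|---|---|
| Table 1: routine-week row, Week 52/104 row, second footnote | 3 | 0 |
| Section 7.3.5 (both paragraphs) | 2 | 0 |
| Section 7.5.1.2 | 1 | 0 |
| Section 7.5.1.3 | 1 | 0 |
| Section 7.5.1.4 | 1 | 0 |
| Section 7.5.1.7.1 | 1 | 0 |
| Section 7.5.1.7.2 | 1 | 0 |
| Section 7.5.1.5.2 (Week 52) | 0 | 1 |
| Section 7.5.1.6.2 (Week 104) | 0 | 1 |
| **Total** | **10** | **2** |

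Otherwise, discharge is timed from the start only for the 48-hour stay after a dose adjustment (Table 1, Sections 7.3.5 and 7.5.1.7.1). That is a different rule.

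**2. Earliest discharge, measured from the start of the infusion**

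Visit text: 1 h. Table 1 and Section 7.3.5: infusion duration + 1 h.

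| Infusion duration | Visit text | Table 1 / 7.3.5 | Where the visit-text time falls |
|---|---|---|---|
| 4 h (initial) | 1 h | 4 + 1 = 5 h | 3 h before the infusion ends |
| 1 h (minimum) | 1 h | 1 + 1 = 2 h | exactly at the end of the infusion |

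At 4 hours the error is obvious. At 1 hour the literal time looks plausible and is easier to miss.

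**3. Shortfall that could actually occur**

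The literal times are not the real exposure, because the Day 1 procedures keep the patient past the end of the infusion. Sections 7.5.1.5.1 and 7.5.1.6.1 and Table 6 require a PK sample as soon as possible after the end, and vital signs, general appearance and skin checks within the following hour. Table 6 puts that window at 4:01 to 5:00 for a 4-hour infusion. Section 7.5.5.1 allows the end-of-infusion PK sample up to +0.5 h.

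Shortfall = 60 min − time after the end of the infusion at which the last required Day 1 item is done.

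- PK sample and checks done at once (1 min): 60 − 1 = 59 min.
- PK sample at its +30 min limit: at most 60 − 30 = 30 min.
- Checks at the end of their window (60 min): 60 − 60 = 0 min.

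**4. Number of infusions**

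Weeks 25 to 104 contain 80 weekly infusions. Two are affected: 2 / 80 = 2.5% per patient. For the planned 9 to 12 patients this is 2 × 9 = 18 to 2 × 12 = 24 infusions, if nobody withdraws.

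**The case against.** The best counter-argument is that the controlling rule already covers these visits. Table 1 is a table of minimum stays with a row for exactly these weeks, and the visit sentence only permits discharge. A site that waits one hour after the end satisfies every text, so no site faces two incompatible duties. The literal reading also cannot be followed, because the Day 1 PK sample and checks come after the end of the infusion. A real shortfall needs a site to overlook Table 1 and Section 7.3.5, depart from its habit at every other visit, finish the checks early and discharge at once. Shortening towards 1 hour is allowed only step-wise, once no further dose increases are expected and the intensified assessments are complete. Caregivers are briefed on delayed reactions and carry an emergency card. On this view the point is purely editorial.

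Most of this stands as to weight. The 3-hour figure should not be read as an exposure, and 18 to 24 is a ceiling on opportunities rather than an expected count. It does not remove the inconsistency. The permission in the visit text is broader than the minimum allows, the Day 1 items can be finished within minutes, and this is an operative visit instruction rather than background text.

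**Conclusion.** The two sentences are wrong as written. They conflict with the Table 1 row for the same weeks and with Section 7.3.5, and the 10-to-2 count leaves little doubt that the end of the infusion was meant.

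The size is a possible shortfall of 0 to about 59 minutes in the post-infusion hour, at 2 of 80 infusions per patient. This assumes a site that relies on the visit text alone; a site that applies Table 1 or Section 7.3.5 has no shortfall. The practical risk is further limited because these infusions are always given at the PI site, dose adjustments are avoided in Weeks 48 to 52 and 100 to 104, and the patient returns on Day 2. Endpoints and analyses are not affected. It should be corrected because it weakens a safety-observation rule for children.

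**What to change.** In protocol Sections 7.5.1.5.2 and 7.5.1.6.2, change the discharge sentence so that the hour runs from *the end* of the infusion instead of its *start*. Leave Table 1 and Section 7.3.5 as they are. The earliest discharge then becomes 5 h after the start for a 4-hour infusion and 2 h for a 1-hour infusion, and all 12 statements agree.

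The cost is a few words in each of two sentences. No procedure, data item or analysis changes, and the SAP needs no edit.
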